3.3 Subject Disposition and Evaluability

A disposition of safety population, the number of subjects discontinuing from treatment, and the primary reason for discontinuation will be summarized. This summary will also be presented by exposure range.

Subject listing will be provided for the disposition of subjects who died during study.

3.4 Demographics and Baseline Characteristics

3.4.1 Demographics and Other Characteristics

Subject demographics information will be summarized. Descriptive statistics will be provided for age, height, weight, body mass index (BMI) and KPS. Frequencies and percentages will be tabulated for gender, child bearing potential, race, and ethnicity.

Demographics and other baseline characteristics will be summarized by treatment group in each population.

3.4.2 Medical History

Medical history will be coded using Medical Dictionary for Regulatory Activities (MedDRA) Version 24.1 terminology, and summarized by Preferred Term (PT). Subject listing will be provided.

Kadmon Corporation

Page 12 of 26

3.5 Concomitant Medications

Concomitant medications will be coded using the World Health Organization Drug Dictionary (WHODrug-Global-B3, version 202109). CM are defined as medications taken after the start of study treatment and during the study period, including those initiated before but ongoing at the start of study treatment. If a medication start date is partially or fully missing and it is unclear as to whether the medication is prior or concomitant, it will be assumed that the medication is concomitant.

Number and percentage of incidence of CM will be summarized according to Anatomical Therapeutic Class (ATC) and preferred drug name.

3.6 Treatment Exposure

The number of subjects will be summarized, along with descriptive summary of duration of treatment, exposure ranges and overall exposure.

The duration of treatment (days) is defined as: (Date of last dose – Date of first dose) + 1. It will also be classified into the following exposure ranges: 0 to 6 months; > 6 to 12 months, > 12 to 18 months, > 18 to 24 months, > 24 to 30 months, > 30 to 36 months and > 36 months.

Overall exposure will be summarized in total patient-years, derived as Exposure in patient (years) = Sum of duration of treatment in days (for all patients in each dose group) / 365.25.

3.7.2 Secondary Efficacy Endpoints

3.7.2.1 Duration of Response (DOR)

DOR will be presented according to 5 methodologies:

- The primary definition of DOR is the time from first documentation of response to the time of first documentation of deterioration from best response (e.g., CR to PR, or PR to LR).
- The secondary definition of DOR is the time from first documentation of response to the time of first documentation of lack of response.
- The tertiary definition of DOR is the time from first documentation of response to the time of initiation of new systemic cGVHD therapy.
- The quaternary definition of DOR is the time from first documentation of response to the time of first documentation of lack of response (as the secondary definition) but with durations summed for multiple response/lack of response episodes.
- The FDA definition of DOR is the time from first documentation of response to the time
 of first documentation of organ-level progression, initiation of a new cGVHD therapy, or
 death from any cause, whichever occurs first

The DOR will be reported for early responders, and statistics will include:

- Kaplan-Meier plots and descriptive statistics of DOR. The censoring rules in Table 2 will be applied
- Landmark analyses: Number and percentage of subjects with response sustained for ≥ 3, ≥ 6, ≥ 9, ≥ 12, ≥ 15, ≥ 18, ≥ 24, ≥ 30, ≥ 36 months

Table 2 Censoring Rules for Duration of Response

DOR	Events	Censoring		
Primary	 Deterioration from best response Initiation of new systemic therapy for cGVHD Death 	 Last documented response assessment If LR or initiation of new systemic therapy happens 		

Kadmon Corporation

Page 15 of 26

Secondary	 Documented LR Initiation of new systemic therapy for cGVHD Death 	immediately after two or more missed response assessments, the event date is set as 24 weeks after last documented response assessment prior this event
Tertiary	 Initiation of new systemic therapy for cGVHD Death 	Last response assessment or long term follow up assessment, whichever is the latest and available
Quaternary	 Documented LR Initiation of new systemic therapy for cGVHD Death With summation of DOR from multiple response episodes 	Same as censoring rules for primary and secondary
FDA defined	 Documentation of organ-level progression Initiation of a new cGVHD therapy Death 	Last documented response assessment If organ-level progression or initiation of new systemic therapy happens immediately after two or more missed response assessments, the event date is set as 24 weeks after last documented response assessment prior this event

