#### 4 STUDY POPULATION

# 4.1 Number of Subjects

Approximately 70 subjects may be enrolled.

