3.7.2.2 Change in Lee Symptom Scale Score (LSS)

The Lee cGVHD Symptom Scale consists 30 items of 7 domains: skin, eyes and mouth, breathing, eating and digestion, muscles and joints, energy, and mental and emotional. Each question is scored 0, 1, 2, 3 or 4.

Kadmon Corporation

Page 16 of 26

A domain score will be calculated for each domain by taking the mean of all items completed if more than 50% were answered and normalizing to a 0 to 100 scale. A summary score will be calculated as average of all non-missing domain scores if more than 50% of them are non-missing. A higher score indicated more bothersome symptoms. 7 points difference on the summary score of cGVHD symptom scale was found to be clinically meaningful. In the above formulas, m is the number of items have non-missing value in a domain, and n is the number of domains have non-missing domain scores.

Raw
$$Score = \frac{I_1 + \dots + I_m}{m}$$
, $Domain Score = (Raw Score/4)*100$

$$Summary Score = \frac{Domain Score_1 + \dots + Domain Score_n}{n}$$

In the above formulas, m is the number of items have non-missing value in a domain, and n is the number of domains have non-missing domain scores.

Analyses will include:

- Both score and change-from-baseline values (summary score and domain scores) will be summarized as continuous variables by visit
- Number and percent of subjects with a ≥7-point reduction from baseline (C1D1)
- Number and percent of subjects with a ≥7- point reduction from baseline on at least 2 consecutive post-baseline assessments.
- Duration of a 7-PtR (DO7-PtR) (defined as time from documentation of the first ≥7-point reduction to the first documentation of less than 7-point reduction). If there are multiple episodes, then DO7-PtR will be measured as the sum of DO7-PtR from all episodes.

These analyses will be performed on Full Analysis Set.

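### Kaplan-Meier on the summed (quaternary) duration of response does not estimate total time in response; with lack of response as an event, it reads too low

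*SAP*

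**What the plan says.** SAP 3.7.2.1 presents duration of response (DOR) in five ways. The secondary definition runs from first response to first LR. The quaternary definition starts from that, "but with durations summed for multiple response/lack of response episodes". The analysis line covers DOR as a whole and makes no exception for the summed version: "Kaplan-Meier plots and descriptive statistics of DOR. The censoring rules in Table 2 will be applied".

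In SAP Table 2 the quaternary row lists documented LR, new systemic cGVHD therapy and death as events, and adds "With summation of DOR from multiple response episodes". Its censoring entry is "Same as censoring rules for primary and secondary": the last documented response assessment, plus the missed-assessment rule under which "the event date is set as 24 weeks after last documented response assessment prior this event".

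The SAP does not say which LR ends the summed time, or how to code a subject who lost response, regained it and is still responding at the last assessment. It also does not say how a date imputed at 24 weeks enters a sum of episodes.

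**The concern.** Kaplan-Meier is valid when censoring is independent of the event on the time scale being analysed. Here that scale is months accumulated in response.

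Take two subjects, each followed for 24 months from first response with no new therapy and no death. One responds throughout and is censored at 24. The other responds for 8 months, is in LR for 8 and responds for another 8, and is censored at 16. Calendar follow-up is the same, but the subject who accumulates response more slowly is censored earlier. Enrolling more subjects does not remove this.

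The event definition adds a second problem. An LR that may be followed by another response does not end total response time, yet Table 2 treats it as an event.

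The quaternary definition differs from the secondary one only in subjects with repeat episodes, and those are the subjects for whom the method fails.

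**Working it through.** The plan gives no DOR figure to reproduce, so the check is a simulation.

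**Target.** Let V(t) be the months spent in response up to calendar time t since first response, T the time of new systemic therapy or death, and C the calendar censoring time. Total time in response is V(T), and the target is P(V(T) > x). The data give V(min(T, C)). Kaplan-Meier on V needs V(C) to be independent of V(T). Both depend on the same response path, so they are dependent even when C is independent of everything else.

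**Inputs.** From the documents: the Table 2 events, the use of Kaplan-Meier, and about 70 subjects (protocol 4.1). Assumed, because the documents give no episode data:

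- Response to LR: 1/18 per month. Response to new therapy or death: 1/60.
- LR back to response: 1/9. LR to new therapy or death: 1/18.
- Cut-off uniform between 12 and 48 months after first response.

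These imply a mean response spell of 1/(1/18 + 1/60) = 13.8 months, a mean LR spell of 1/(1/9 + 1/18) = 6 months, and re-response after (1/9)/(1/9 + 1/18) = 2/3 of LR spells.

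**True value.** One third of LR spells end in therapy or death. Per month in response, the rate of finishing for good is 1/60 + (1/18)(1/3) = 0.01667 + 0.01852 = 0.03519. Hence P(V(T) > x) = exp(−0.03519x): exp(−0.422) = 65.6%, exp(−0.844) = 43.0% and exp(−1.267) = 28.2% at 12, 24 and 36 months.

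**Kaplan-Meier on the sum**, 120,000 simulated subjects, under two codings that keep LR as an event:

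| Months in response | True | LR at cut-off is an event | Difference (points) | Any LR is an event | Difference (points) |
|---|---|---|---|---|---|
| > 12 | 65.6% | 63.1% | −2.5 | 60.6% | −5.0 |
| > 24 | 43.0% | 37.6% | −5.4 | 28.9% | −14.1 |
| > 36 | 28.2% | 20.9% | −7.3 | 9.0% | −19.2 |

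Therapy and death are events in both codings. In the any-LR coding, a subject who lost and regained response is an event at the summed time even if still responding.

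**Other assumptions.** Seven further scenarios of 40,000 subjects used response episodes of 8 or 12 months, LR gaps of 4 or 6 months, 30% to 100% of subjects able to re-respond, and between-subject heterogeneity from none to strong. Both codings were below the truth in all seven:

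| Landmark | LR at cut-off (points) | Any LR (points) |
|---|---|---|
| 12 months | −0.4 to −4.5 | −1.1 to −11.1 |
| 24 months | −0.8 to −7.3 | −3.2 to −18.1 |

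The smallest values came from a scenario in which 18% of subjects had more than one episode. If nobody re-responds, the sum is a single episode and the bias disappears.

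**Sampling error.** In the base case with 50 responders, the standard deviation of the Kaplan-Meier estimate (LR at cut-off as event) is 6.7 points at 12 months and 8.2 at 36. Only 5.0% of simulated subjects remain at risk at 36 months: 0.05 × 50 = 2.5 to 0.05 × 70 = 3.5 subjects.

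**Does the alternative work?** In two of the seven scenarios, the area under a censoring-weighted probability-of-being-in-response curve over 24 months was 11.06 against a true 11.08 months, and 11.76 against 11.76.

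**The case against.** The strongest reply is that little depends on this curve. It is one of five DOR presentations in a study with no formal hypothesis (protocol 9.1) and no power calculation (protocol 9.2). The single-episode curve is already planned. At 12 months the base-case bias with LR at cut-off as the event is well inside sampling error, and splitting about 70 subjects over three dose groups widens that error further. Every rate is assumed. All of this stands and limits the weight of the point. It does not make the method valid: bias does not shrink with more subjects, and a confidence interval does not show it.

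Three stronger readings are tempting, and the documents do not support them.

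- A reader might infer that the bias could go either way. Coding only new therapy or death as an event does give an upward bias (66.8%, 46.1% and 32.9% in the base case). That coding drops documented LR, which Table 2 lists as an event.
- A reader might extend the figures to the landmark summary. The SAP words it as "Number and percentage of subjects with response sustained for" given numbers of months. These are counts and are not said to be read from the Kaplan-Meier curve.
- A reader might include the Lee Symptom Scale duration, for which SAP 3.7.2.2 states "If there are multiple episodes, then DO7-PtR will be measured as the sum of DO7-PtR from all episodes". No Kaplan-Meier analysis is specified for it, so the argument does not carry over.

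One objection to the remedy also stands. Response is assessed only at Baseline and the three-monthly treatment visits (protocol Appendix A). Long-term follow-up records survival, new systemic therapy and relapse (protocol 6.2.5), and subjects who enter in long-term follow-up have only those assessments (protocol 6.2.2). Response status is therefore unknown once assessments stop, and any replacement must allow for that.

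**Conclusion.** The point holds for the quaternary DOR curve alone. Kaplan-Meier with single-episode censoring rules, applied to summed episodes, does not estimate total time in response. With LR as an event the curve understates it in every scenario run. That direction is a simulation finding, not a general proof.

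The principle needs no assumed rates, but the size does. In the base case the shortfall grows from 2.5 to 7.3 points between 12 and 36 months if LR at cut-off is the event, and from 5.0 to 19.2 points if any LR is. It can be under 1 point, with LR at cut-off as the event, when few subjects re-respond. The wide gap between the two codings is a practical matter in itself, because the SAP does not choose between them.

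This is a moderate problem of interpretation in a descriptive study, and worth correcting because the change is cheap.

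**What to change.** In SAP 3.7.2.1 and Table 2, do not run Kaplan-Meier on the summed quaternary duration. Instead:

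1. Report a probability-of-being-in-response curve on calendar time since first response. Allow subjects to move between response and LR, and make new systemic therapy and death absorbing states.
2. Censor at the last response assessment, since response is not assessed in long-term follow-up. State how a therapy start or death after that assessment is handled, and restate or drop the 24-week rule for this analysis.
3. Report the area under the curve as mean time in response to a fixed horizon that follow-up supports, with a bootstrap 95% CI.
4. Keep Kaplan-Meier for the single-episode secondary definition.

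The cost is SAP wording and some extra programming, with no new data. There are two downsides. The summary becomes a mean time in response and no longer a distribution of durations. Censoring at the last response assessment also assumes that stopping assessments is unrelated to later response, which may not hold for subjects who stop treatment, so the report should say so.

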# 5.2 Dosage and Administration

Subjects will be treated with the same dosage of belumosudil as they were assigned in Study KD025-208 or Study KD025-213:

- Study KD025-208: belumosudil 200 mg QD, belumosudil 200 mg BID, or belumosudil 400 mg QD
- Study KD025-213: belumosudil 200 mg QD or belumosudil 200 mg BID

Belumosudil will be tapered after a sustained response for 6 months and cessation of all other immunosuppressants for at least 3 months. Tapering is also expected if subjects withdraw for reasons other than cGVHD progression or adverse events. The tapering schedule for belumosudil is as follows:

- 200 mg QD  $\rightarrow$  200 mg QOD for 1 month $\rightarrow$  Discontinue
- 200 mg BID → 200 mg QD for 1 month → 200 mg QOD for 1 month → Discontinue
- 400 mg QD → 200 mg QD for 1 month → 200 mg QOD for 1 month → Discontinue

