#### 6.2.2 Baseline Visit

Subjects will be evaluated to determine if they meet all inclusion/exclusion criteria. Those signing the ICF will be enrolled in the study.

Note: If the subject was in LTFU in Study KD025-208 or in Study KD025-213, the subject will only have LTFU assessments performed once approximately every 3 months (Section 6.2.5).

Belumosudil will be administered as follows:

- Subject receives same dose of belumosudil as assigned in Study KD025-208 or in Study KD025-213, as appropriate. The first dose may be taken at home or in the clinic.
- Dispense a study drug diary to the subject

The following data will need to be captured from Study KD025-208 or Study KD025-213:

- The dosing group to which the subject was assigned or randomized
- Clinician-reported Global cGVHD Activity Assessment from Day 1
- Any ongoing AEs

The following efficacy assessments will be performed:

Clinician-reported Global cGVHD Activity Assessment

- Response assessment. (Note: all responses will be assessed with respect to Cycle 1 Day 1 of Study KD025-208 or Study KD025-213.)
- PFT (for subjects with lung cGVHD or when lung cGVHD is suspected)
- LSS
- Use of corticosteroid dosage
- Use of other cGVHD therapies

The following safety assessments will be performed:

- Symptom-directed PE
- Vital signs
- Weight and height
- KPS
- Hematology lab testing
- Clinical chemistry lab testing
- 12-lead ECG
- Urine pregnancy test (any positive results will be confirmed with serum testing)
- Use of concomitant medications
- AEs

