3.1.3.1 Reporting of Numerical Values

Continuous data will be described using descriptive statistics: number of observations (n), mean, standard deviation, median, minimum and maximum. Frequencies and percentages will be used for summarizing categorical data. When categorical data are presented, the percent will

Kadmon Corporation

Page 9 of 26

be suppressed when the count is zero in order to draw attention to the non-zero counts. The denominator for all percentages, unless otherwise specified, will be the number of subjects in the specified analysis population or group.

Means, medians, standard deviations, and confidence intervals will be reported to one decimal place more than the data reported on the case report form (CRF) or by the laboratory/vendor. Minimum and maximum will be reported to the same number of decimal places displayed on the CRF or by the laboratory/vendor. P-Values will be reported to 4 decimal places.

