3.1.6 Handling of Incomplete or Missing Data

Missing data will not be imputed in general and it will be reported as missing in all listings. For categorical variables, patients with missing data are not included in calculations of percentages unless otherwise specified.

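### Duration-of-response landmarks are planned as crude percentages with no censoring rule, so the landmark table will read low against Kaplan-Meier in the same subjects

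*SAP*

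**What the plan says.** SAP 3.7.2.1 lists two outputs for DOR.

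- The first is a time-to-event analysis: "Kaplan-Meier plots and descriptive statistics of DOR. The censoring rules in Table 2 will be applied".
- The second is a set of landmark analyses at 3, 6, 9, 12, 15, 18, 24, 30 and 36 months, defined as "Number and percentage of subjects with response sustained for" at least that long. The Table 2 censoring rules are attached to the first output, not to this one.

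The group for both is given by "The DOR will be reported for early responders", a term the SAP does not define.

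Two general rules could govern the landmark percentages. SAP 3.1.3.1 says "The denominator for all percentages, unless otherwise specified, will be the number of subjects in the specified analysis population or group". SAP 3.1.6 says that, for categorical variables, "patients with missing data are not included in calculations of percentages unless otherwise specified". The SAP does not say whether a DOR censored before a landmark counts as missing.

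Table 2 censors the primary, secondary, quaternary and FDA definitions at the last documented response assessment. Only the tertiary definition, time to new systemic therapy, may also be censored at a long-term follow-up (LTFU) contact.

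**The concern.** A responder last assessed in response at month 20 has not been shown to hold response for 24 months, and has not been shown to lose it either. A simple percentage has no place for such a person. Under the default denominator, that responder sits in the same cell as someone whose response ended.

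Censoring of this kind is built into the design. Protocol 6.2.5 limits LTFU to survival, new systemic cGVHD therapy and relapse. The Schedule of Assessments has response assessed only at Baseline and the three-monthly treatment visits. For subjects who enter already in LTFU, Protocol 6.2.2 states that "the subject will only have LTFU assessments performed once approximately every 3 months". Protocol 5.2 adds that "Belumosudil will be tapered after a sustained response for 6 months and cessation of all other immunosuppressants for at least 3 months" (section 4.6 words the taper as optional). Some responders may therefore leave response assessment because their response held.

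Landmark percentages from a long-term extension are likely to be quoted on their own, without the curve. If they are low because of follow-up rather than loss of response, the table and the curve in the same report will disagree.

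**Working it through.** The documents state no DOR rate and no censoring distribution for KD025-217, so there is no planned figure to reproduce. The check is of what each possible landmark figure estimates. The denominator is taken to be responders; if the Full Analysis Set were used, non-responders would be mixed in as well.

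**Notation.** S(t) is the probability that response is sustained to t. G(t) is the probability of still being under response follow-up at t. Censoring is assumed independent of DOR.

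**1. What each figure targets.**

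- Kaplan-Meier: S(t).
- Percentage with censored responders kept in the denominator (SAP 3.1.3.1): S(t) × G(t). The shortfall is S(t) − S(t)G(t) = S(t) × (1 − G(t)).
- Percentage with censored responders excluded (SAP 3.1.6): S(t)G(t) / [S(t)G(t) + E(t)], where E(t) is the probability of an event that occurs before t and before censoring. Everyone with an event before t had at least probability G(t) of being observed to have it, so E(t) ≥ G(t)(1 − S(t)). The ratio therefore cannot exceed S(t). Early events stay in while responders censored early drop out.

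Both readings are low, or equal to Kaplan-Meier when nothing is censored before t.

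**2. Simple illustration at 24 months.** Assume S(24) = 0.40.

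- G(24) = 0.90: 0.40 × 0.90 = 36%, a gap of 4 points.
- G(24) = 0.60: 0.40 × 0.60 = 24%, a gap of 16 points.

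**3. Range at 36 months.** Assume exponential DOR and exponential censoring, with S(36) of 0.40 or 0.60 and G(36) from 0.8 to 0.2.

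| S(36) = Kaplan-Meier | G(36) | Kept in denominator | Gap (points) | Excluded | Gap (points) |
|---|---|---|---|---|---|
| 60% | 0.8 | 48% | 12 | 57.0% | 3.0 |
| 60% | 0.6 | 36% | 24 | 52.9% | 7.1 |
| 60% | 0.4 | 24% | 36 | 46.9% | 13.1 |
| 60% | 0.2 | 12% | 48 | 36.1% | 23.9 |
| 40% | 0.8 | 32% | 8 | 36.9% | 3.1 |
| 40% | 0.6 | 24% | 16 | 33.0% | 7.0 |
| 40% | 0.4 | 16% | 24 | 27.6% | 12.4 |
| 40% | 0.2 | 8% | 32 | 19.3% | 20.7 |

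Worked row, S(36) = G(36) = 0.6: the two hazards are equal, so E = 0.5 × (1 − 0.36) = 0.32, and 0.36 / (0.36 + 0.32) = 52.9%.

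**4. Small-sample check.** With 50 responders, S(36) = 0.60, G(36) = 0.6 and 4,000 simulated data sets, the mean Kaplan-Meier estimate at 36 months was 59.9% and the mean crude percentage 35.9%.

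**5. Pattern over time.** As a share of the Kaplan-Meier value, the kept-in-denominator shortfall is 1 − G(t), which can only grow with the landmark. In points, it is larger at 24 and 36 months than at 12 in all eight scenarios (5 to 35 points at 12 months), although in two of them it peaks at 24.

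**The case against.** **Kaplan-Meier is already planned.** It is the item directly above, with explicit censoring rules, and the count can be read as a tally of observed durations. This stands in part. A reader might infer that the DOR analysis as a whole understates durability; the documents do not support that. What is affected is the landmark table, because no Kaplan-Meier landmark probabilities or intervals are specified for DOR and a curve does not correct a printed percentage.

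**The SAP never says that censored responders are failures.** True. It follows from the default denominator in 3.1.3.1, and 3.1.6 could be read to exclude them. The direction is the same either way.

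**Censoring before 24 months may be light.** Protocol 1.4.2 puts the KD025-213 cutoff of 19 February 2020 six months after the last subject's first visit. The main cohort had therefore started by about August 2019, roughly two years before the protocol amendment of 8 September 2021 that the SAP follows. The interim (Protocol 9.6) waits for 3 years of treatment or earlier withdrawal, companion subjects apart. This stands against assuming heavy administrative censoring at 24 months in continuing main-cohort subjects. It does not cover companion subjects or those who stop drug without an event. It also does not secure the 36-month landmark at the interim: DOR starts at first response, so 3 years of treatment gives 3 years minus the time to response.

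**Dose groups.** Median follow-up at that cutoff was 28.8 months in KD025-208 and 7.9 months in KD025-213, and a reader might infer that dose comparisons are distorted throughout. But both 200 mg groups pool the two parent studies, and the KD025-213 arms had 8.0 and 7.9 months. The contrast is plausible mainly for 400 mg QD, which comes only from KD025-208.

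**Kaplan-Meier is not the truth either.** This stands. Subjects enter the extension on drug or in LTFU without a failure-free-survival event, which favours durable responses, and censoring after stopping drug may be informative. Kaplan-Meier removes neither problem.

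**Conclusion.** The point holds for the landmark table. As written, the DOR landmark percentages are biased low relative to Kaplan-Meier in the same subjects whenever responders are censored before the landmark, under either general rule for the denominator. This assumes that censoring is independent of DOR.

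The direction follows from the text and that assumption. The size does not, because S(t) and G(t) are not in the documents. A gap of 4 to 16 points at 24 months is a fair illustration for S(24) = 40% with 90% to 60% still followed; the wider ranges above show sensitivity and are not forecasts. The relative shortfall is greatest at late landmarks. It should matter most for the four definitions censored at the last response assessment and less for the tertiary definition, whose follow-up continues through LTFU.

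The documents do not support saying that long-term durability is understated overall, or understated relative to all parent-study responders. Selection into the extension acts in the opposite direction, so the net direction against that wider group is not fixed.

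**What to change.** In SAP 3.7.2.1, replace the landmark item with Kaplan-Meier probabilities of sustained response at the same nine times, each with a 95% confidence interval and the number at risk, for the primary, secondary, tertiary and FDA definitions, using the Table 2 censoring rules.

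If counts and percentages are kept, label them as observed and state the denominator, which requires a definition of early responder. At each landmark, show three counts separately: sustained, event before the landmark, and censored before the landmark. Use this layout for the quaternary definition in any case, because it sums several response episodes and a standard Kaplan-Meier estimate is not straightforward there.

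Add one sentence of interpretation: the estimates apply to subjects enrolled in the extension, and censoring after stopping drug may be informative.

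The cost is a few sentences in the SAP and standard output from the Kaplan-Meier analysis already planned. No new data are needed.
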